9.0 Investigational drugs

9.1 CT-011

CT-011 (humanized monoclonal antibody) for parenteral administration is supplied as a 20 mg/mL clear solution in phosphate buffer saline and is preservative-free. The drug product is packaged in depyrogenated clear 6-mL glass vials (type 1 neutral glass) sealed with Tefloncoated gray chlorobutyl rubber stoppers and sealed with aluminum seals. Each vial consists of 5.25 mL of approximately 20 mg/mL CT-011.

Label Of The Drug: The container label and the immediate outer carton label of the marketed product to be used in the clinical study will contain the following information: product name and strength, lot number, protocol number, vial number, manufacturer’s name and address, recommended storage conditions, and an investigational caution statement.

Storage Of The Drug: The vials of CT-011 MUST be kept frozen as per US Pharmacopoeia, between -13°F to 5°F until use. Prior to planned infusion, the CT-011 drug product vial(s) must be thawed at room temperature for approximately 1 hour. Once thawed, the drug product should be diluted immediately into an infusion bag and administered to the patient as soon as possible. It is important to note that the thawed vials of CT-011 drug product can be held refrigerated at 2°C to 8°C (35°F to 46°F) for no longer than 7 days, though it is advised to use the thawed drug product immediately. The thawed drug product vials must not be frozen again. The infusion bag containing

CT-011 can be stored at room temperature for no longer than 2 hours prior to the initiation of infusion, though it is advised to administer drug product immediately. CT-011 vials or infusion bags that are not stored as described above (e.g. at longer periods of time or at higher temperatures) must not be used and must be discarded according to the Center's policy for handling of unused drugs and only after drug accountability monitoring has been performed.

Preparation of CT-011 For Administration: The solution will be prepared by a pharmacist, the Investigator, or a study nurse. Appropriate aseptic techniques should be used. Prior to infusion the vial(s) must be thawed at room temperature for approximately 1 hour; the vial(s) should be swirled gently to make sure that the solution is clear, colorless, and transparent. **DO NOT SHAKE!** Effort must be made so that once thawed; the drug will be diluted immediately into an infusion bag and administered to the patient as soon as possible (see Section 8.3 for drug product storage conditions). Each vial contains **approximately** 20 mg/mL CT-011. While most lots will be provided at this concentration, note that current specifications allow for a concentration range of 19mg/ml to 21mg/ml. Determine the total amount of CT-011 required based on the drug handling sheet provided keeping in mind that maximal total dose allowed is 600mg per patient

The appropriate amount of CT-011 solution should be withdrawn from the vial(s) and added to an infusion bag containing 250 mL of 0.9% sodium chloride solution, USP. The bag will be identified with the patient number. The bag should then be gently inverted to mix the solution in order to avoid foaming. Parenteral solutions should be inspected visually for particulates and discoloration prior to administration. Once the infusion is prepared, it should be administered immediately.

Method of Administration: CT-011 will be administered intravenously on day 3 of each 28 day cycle. The drug is diluted into a 250mL saline bag which in the FIRST infusion is administered in a step-wise manner: 50ml/hr for 30min; 100ml/hr for 30min; 150ml/hr for 30 min and 200ml/hr till the end (another ~30min) for an approximate time of 2hrs. If no infusion related AEs occurs the first time, subsequent administrations are at 200mL/hr which will deliver the drug over approximately 1:15hrs. In the event that Grade 3 or higher toxicity occurs during infusion, administration of CT-011 should be stopped immediately. Administration of CT-011 could be resumed only after the toxicity has resolved using the slowest rate of infusion (50mL/hr). Vital signs will be measured prior to infusion and every 15 minutes for the first hour, then every 30 minutes for an additional hour, and then once an hour until the end of infusion.

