- If ≥ 2 patients in cohort 4 exhibit a DLT at the dose of 6 mg/kg CT-011 in combination with lenalidomide 25 mg, 3 more patients will be enrolled at the 6 mg dose of CT-011 in combination with 15 mg lenalidomide. If there is < 1 DLT with CT011 6mg/kg and lenalidomide 15 mg, this will be defined as the MTD. If there are 2 or more DLT, then 3 additional patients will be enrolled at the CT-011 6mg/kg and lenalidomide 10 mg, which will become the MTD

To determine dose escalation, we will focus on the number of patients who experience dose limiting toxicity; i.e. a patient who experiences more than one DLT will be counted only once.

Discontinuation of treatment due to disease progression will not constitute a DLT.

In the Phase 1 portion of the study, subjects who withdraw or prematurely discontinue treatment before completing the first treatment cycle for reasons other than toxicity and DLT will be replaced.

After 4 cycles of therapy or earlier if clinically indicated, response determination will be assessed by the IMWG criteria. At the end of Cycle 4, if a subject has responded (complete or partial response) or has stable disease, dosing with CT-011, lenalidomide and dexamethasone(if initiated after cycle 1-2) will continue for a minimum of 8 additional cycles or until withdrawal.

For the Phase II portion

Upon determination of the MTD in the phase I portion of this trial, the phase II portion of the study will commence enrollment at the MTD determined in the phase I portion with CT-011 in combination with lenalidomide. In the event that a MTD is not established, safety and tolerability data collected in the Phase I portion of the study will guide decisions on dosing of CT-011 in the phase II trial.

Dexamethasone 40 mg orally weekly may be added if only stable disease after 3 cycles according to the IMWG criteria (section13). Dexamethasone can be reduced to 20 mg based on tolerability or if patient is 70 years or older.

During the phase II portion of this trial, we will not evaluate patients for DLTs as was done in the phase I portion; however, we will use the DLT criteria to identify potential toxicity and tolerability concerns occurring at any cycle to initiate further evaluation to ensure safety of patients. An independent Data and Safety Monitoring Committee will continue oversight of this trial. See Appendix E for details.

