5 TREATMENT PLAN AND PROCEDURES

For the Phase I portion, this is a standard 3+3 design over 4 dose levels of 1.5, 3, 3, and 6 mg/kg of CT-011 given intravenously every 4 weeks (every 28 days) on day 3, and lenalidomide given at 15, 15, 25, and 25 mg orally daily on days 1-21 of a 28-day cycle. The study drug CT-011 and lenalidomide can be escalated or de-escalated independently of one another as described in the Table below. Twelve to 30 patients will be recruited in the phase I portion of the trial. The phase II portion will utilize the 6 patients treated at the MTD in the phase I portion and an additional 23 patients will be accrued. Dexamethasone 40 mg orally weekly may be added if only stable disease after 3 cycles according to the IMWG response criteria (section 13-0). Dexamethasone can be reduced to 20 mg based on tolerability or if patient is 70 years or older.

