5.1.3 Route and Method of Administration

CT-011 will be administered intravenously on day 3 of a 28 day cycle.

CT-011 is to be administered intravenously using a peripheral line or a central device if such has been inserted. Patients will be dosed on a mg/kg basis.

The first time CT-011 is to be administered intravenously at a dose of 1.5/3.0/6.0mg/kg delivered over approximately 2 hours as follows:

1. Initial rate of infusion is 50 mL/hr for 30 minutes; If no symptoms related to infusion appear:
2. Increased rate to 100 mL/hr; for 30 minutes; If no symptoms appear:
3. Increased rate to 150 mL/hr for 30 minutes; If no symptoms appear:
4. Increase rate to 200 mL/hr for 30 minutes;

In the event that Grade 3 or higher infusion-related toxicity occurs during infusion, administration of CT-011 should be stopped immediately. Administration of CT-011 could be resumed only after the toxicity has resolved using the slowest rate of infusion (50mL/hr). Once the infusion is resumed, vital signs will be checked every 15 minutes for the first hour, then every 30 minutes till the end of the infusion and then one hour from end of infusion.

If no drug related or infusion related adverse events occur during the first administration, further CT-011 administrations could be delivered over approximately 1:15 hours at a rate of 200mL/hr. Subsequent administrations should be made as scheduled in the absence of Grade 3 or higher adverse events or disease progression.

The maximal administration rate is approximately 250 mg/hr. The total dose administered and the dosing rate will be documented in the patient's medical records.

To ensure complete delivery of CT-011, the IV infusion line must be flushed with 0.9% sodium chloride. The following are two recommended methods for flushing the CT-011 IV infusion line:

- 1) When the CT-011 infusion is complete, add an additional 50mL of 0.9% sodium chloride for

injection to the CT-011 infusion bag. Continue the infusion until a volume equal to that of the volume contained in the tubing has been administered.

- 2) Replace the empty CT-011 infusion bag with a 50mL bag of 0.9% sodium chloride for injection and infuse a volume equal to the volume contained in the tubing. Please note: the flush is not included in the total recommended infusion times.

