5.1.5 CT-011 Dose Adjustments

The phase I study showed that CT-011 was well tolerated with no treatment related toxicity at all dose level⁵⁰. Specifically no hematologic toxicity was seen. No dose adjustments or modifications will be made with CT-011 except If DLT was seen with CT-011 at 3 mg/kg in combination with lenalidomide 5 mg, then CT-011 will be reduced to 1.5 mg/kg with lenalidomide 5 mg, which will be the DLT. If adverse events occur that require holding CT-011, the dose will remain the same once treatment resumes. If CT-011 is held for more than 4 weeks, then patient will be taken off study.

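### The 600 mg CT-011 maximum stands only in section 9.1 and conflicts with mg/kg dosing for patients above 100 kg at the 6 mg/kg level

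*Combined protocol and SAP*

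**What the plan says.** Dosing by weight is the rule throughout the design and treatment sections. Section 5 describes a "standard 3+3 design over 4 dose levels of 1.5, 3, 3, and 6 mg/kg of CT-011", Table 5-1 lists the same levels by cohort, and section 5.1.3 states "Patients will be dosed on a mg/kg basis". Section 5.1.5 adds "No dose adjustments or modifications will be made with CT-011 except If DLT was seen with CT-011 at 3 mg/kg"; the exception applies where lenalidomide is at 5 mg. None of these places mentions an absolute ceiling in mg, and section 3 sets no upper body weight.

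Section 9.1, under the preparation instructions, says "Determine the total amount of CT-011 required based on the drug handling sheet provided" and continues "keeping in mind that maximal total dose allowed is 600mg per patient". It does not say whether this applies to one infusion or to the whole course. The drug handling sheet is not part of the documents.

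On frequency and duration, section 9.1 has "CT-011 will be administered intravenously on day 3 of each 28 day cycle". Section 4.3 says that for patients with response or stable disease after cycle 4, dosing "will continue for a minimum of 8 additional cycles or until withdrawal".

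**The concern.** A patient above 100 kg assigned 6 mg/kg meets two instructions that cannot both be followed. Section 5 calls for more than 600 mg and allows no adjustment; section 9.1 forbids more than 600 mg.

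The conflict falls at the top of the CT-011 range: cohort 4, the combinations of 6 mg/kg with a lower lenalidomide dose in section 4.3, and phase II if it runs at 6 mg/kg. Sections 2.3 and 6.1.1 define the MTD by at most 1 DLT among 6 patients at a dose level. With so few patients, each one's actual dose matters to what the level is taken to show. A capped patient would be counted as evidence about 6 mg/kg after receiving less. The same mislabelling would enter the comparison in section 8.1 of CT-011 PK with the earlier single-agent study, and the phase II response rate if phase II is run at that dose.

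The wording also leaves open whether the limit is per infusion or cumulative, and the two readings have very different consequences.

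**Working it through.** **Inputs from the documents.** Limit 600 mg (9.1). Dose levels 1.5, 3 and 6 mg/kg (Table 5-1). One infusion per 28-day cycle (5.1.3, 9.1). At least 4 + 8 = 12 infusions for patients with response or stable disease who do not withdraw (4.3). Primary response assessment after 4 cycles (6.1.2). The documents do not derive the 600 mg, so there is no calculation to reproduce; it equals 6 mg/kg × 100 kg.

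**Assumed inputs.** Body weight is not given. I use 50 to 120 kg for the infusion counts, and normal weights with mean 78 to 86 kg and SD 16 to 20 kg for the proportion above 100 kg.

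**Step 1: per-infusion reading, where the limit binds.** Weight = 600 / dose.

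- 6 mg/kg: 600/6 = 100 kg
- 3 mg/kg: 600/3 = 200 kg
- 1.5 mg/kg: 600/1.5 = 400 kg

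Only the 6 mg/kg level is affected at plausible weights.

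**Step 2: delivered dose at the 6 mg/kg level.** Delivered = 600 / weight.

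- 110 kg: 600/110 = 5.45 mg/kg (9% below 6)
- 120 kg: 600/120 = 5.0 mg/kg (17% below 6)

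**Step 3: how often cohort 4 would contain a capped patient.** Let q be the proportion above 100 kg. P(at least one of six) = 1 − (1 − q)^6. The shortfall for a capped patient is 1 − 100/weight, averaged over weights above 100 kg.

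| Assumed mean, SD (kg) | q | P(at least 1 of 6) | Mean shortfall if capped |
|---|---|---|---|
| 78, 16 | 0.085 | 0.41 | 6.5% |
| 82, 18 | 0.159 | 0.65 | 8.2% |
| 86, 20 | 0.242 | 0.81 | 9.9% |

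If phase II runs at 6 mg/kg, the expected number capped among 29 is 29q: 2.5, 4.6 and 7.0.

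**Step 4: cumulative reading.** Full infusions = whole part of 600 / (dose × weight).

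| Weight (kg) | 1.5 mg/kg | 3 mg/kg | 6 mg/kg |
|---|---|---|---|
| 50 | 8 | 4 | 2 |
| 60 | 6 | 3 | 1 |
| 80 | 5 | 2 | 1 |
| 100 | 4 | 2 | 1 |
| 120 | 3 | 1 | 0 |

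Twelve infusions within 600 mg need a weight of at most 600/(12 × dose), that is 33, 17 or 8 kg at 1.5, 3 or 6 mg/kg. Even the four infusions before the primary assessment need at most 600/(4 × dose), that is 100, 50 or 25 kg. A cumulative limit therefore cannot coexist with the planned 12 infusions at any assumed weight.

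**The case against.** The strongest defence is that a per-bag ceiling can sit alongside mg/kg dosing. The sentence is about preparing one bag, the next step puts that amount into one infusion bag, and section 5.1.3 uses the term total dose for what is given at an administration. The treatment sections are silent on a ceiling rather than ruling one out. Every bag is prepared under section 9.1 with a handling sheet that may settle the point. The effect is also small on average: under the same assumed weights, the dose loss averaged over all patients is 0.6% to 2.4%, and section 9.1 itself accepts vial concentrations 5% either side of 20 mg/mL.

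Much of this stands. The per-infusion reading is the natural one, cohorts 1 to 3 are untouched, and the average shortfall is modest. It does not remove the conflict: section 5.1.5 excludes CT-011 dose changes apart from one DLT-related case, so the treatment section is not merely silent. A handling sheet outside the protocol cannot reconcile two protocol sections.

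Some stronger conclusions are tempting but unsupported:

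- A reader might infer that dosing stops after a few infusions. That needs the cumulative reading, which the context speaks against. The number of infusions would also depend on body weight, which the documents do not give.
- A reader might infer that the 6 mg/kg level would be cleared on patients who never received it. At least one capped patient among six is far from most or all of them.
- A reader might infer that sites will dose differently. Nothing in the documents shows that any site would prepare bags from section 5 alone.
- A reader might infer that a planned dose-normalised PK analysis is compromised. Section 8.1 plans PK parameters and a comparison with the earlier study; it states no dose normalisation.

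**Conclusion.** The point holds in a narrow form. The 600 mg limit appears only in section 9.1 and is incompatible with Table 5-1, 5.1.3 and 5.1.5 for patients above 100 kg at 6 mg/kg. That threshold is exact and needs no assumption. Who is affected is not known from the documents: a 41% to 81% chance of at least one capped patient in a six-patient cohort 4, and roughly 2 to 7 of 29 in phase II if it runs at 6 mg/kg, rest wholly on the assumed weights. The shortfall averages under 10% among capped patients and is larger in the heaviest.

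The cumulative reading is an ambiguity of wording, not the evident intent. It still deserves closing, because the literal text cannot be squared with 12 infusions (0 to 8 would fit over 50 to 120 kg, depending on dose level).

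This is more than missing detail, since a dose-finding trial states the dose at its highest CT-011 level in two conflicting ways. No view is taken here on which instruction is right.

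**What to change.** Reconcile section 9.1 with Table 5-1, 5.1.3 and 5.1.5. State whether the 600 mg limit is per infusion, cumulative or void, and use the same wording in section 5 and section 9.1. The choice is the sponsor's.

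If a per-infusion limit stays:

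- derive delivered mg/kg from the total dose that 5.1.3 already requires to be recorded, together with body weight;
- flag capped patients in the cohort 4 DLT table, so that the MTD decision is read with the delivered doses in view;
- use delivered dose in the section 8.1 comparison with the earlier single-agent study.

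The cost is one clarifying sentence in two sections and an extra line in the DLT and PK tables. It needs no extra patients or visits, and the only input beyond the recorded total dose is the body weight already needed for mg/kg dosing.

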9.2 LENALIDOMIDE (Revlimid™)

Lenalidomide (REVLIMID®), a thalidomide analogue, is an immunomodulatory agent with anti-angiogenic properties. The chemical name is 3-(4-amino-1-oxo 1,3-dihydro -2H-isoindol-2-yl) piperidine-2,6-dione. Lenalidomide has been studied extensively in myeloma and it is approved for use in newly diagnosed and in relapsed MM.

Supply: REVLIMID® (lenalidomide) is available in 5, 10, 15 and 25 mg capsules for oral administration. Each capsule contains lenalidomide as the active ingredient and the following inactive ingredients: lactose anhydrous, microcrystalline cellulose, croscarmellose sodium, and magnesium stearate. The 5 mg capsule shell contains gelatin, titanium dioxide and black ink. The 10 mg capsule shell contains gelatin, FD&C blue #2, yellow iron oxide, titanium dioxide and black ink.

Elimination: The metabolic profile of lenalidomide in humans has not been studied. In healthy volunteers, approximately two-thirds of lenalidomide is eliminated unchanged through urinary excretion. The process exceeds the glomerular filtration rate and therefore is partially or entirely active. Half-life of elimination is approximately 3 hours.

Pregnancy: Due to its structural similarities to thalidomide, a known human teratogen, lenalidomide is contraindicated in pregnant women and women capable of becoming pregnant. When there is no alternative, females of childbearing potential may be treated with lenalidomide provided adequate precautions are taken to avoid pregnancy. Females must commit either to abstain continuously from heterosexual sexual intercourse or to use two methods of reliable birth control, including at least one highly effective method (e.g., IUD, hormonal contraception, tubal ligation, or partner's vasectomy) and one additional effective method (e.g., latex condom, diaphragm, or cervical cap), beginning 4 weeks prior to initiating treatment with REVCLIMID® (lenalidomide), during therapy with REVCLIMID® (lenalidomide), during therapy delay, and continuing for 4 weeks following discontinuation of REVCLIMID® (lenalidomide) therapy. If hormonal or IUD contraception is medically contraindicated, two other effective or highly effective methods may be used.

Deep Venous Thrombosis and Pulmonary Embolism: This drug has demonstrated a significantly increased risk of DVT and PE in patients with multiple myeloma who were treated with REVCLIMID® (lenalidomide) combination therapy. Patients and physicians are advised to be observant for the signs and symptoms of thromboembolism. Patients should be instructed to seek medical care if they develop symptoms such as shortness of breath, chest pain, or arm or leg swelling. Prophylactic anticoagulation or antiplatelet therapy prescribed in conjunction with REVCLIMID® (lenalidomide) is required for patients enrolled in this current trial.

10.0 PATIENT SAFETY

10.1 Monitoring of Adverse Events

Significant adverse events should be identified and recorded. Seriousness, expectedness, and causality will be assessed using the definitions that follow. The descriptions and grading scales found in the revised NCI Common Terminology Criteria for Adverse Events (CTCAE) version 4.0 will be utilized for adverse event reporting.

10.2 Definitions of Adverse Events and Causality

An **Adverse Event (AE)** is any untoward medical occurrence in a patient administered a pharmaceutical product and which does not necessarily have to have a causal relationship with the treatment. For marketed products in the U.S., a **Serious Adverse Event (SAE)** is any untoward medical occurrence that at any dose:

- Results in death (if the patient's death is suspected as being a direct outcome of the adverse event)
- Is life-threatening (the patient was at substantial risk of dying at the time of the adverse event or it is suspected that the use or continued use of the product would result in the patient's death)
- Requires inpatient hospitalization or prolongation of existing hospitalization
- Results in persistent or significant disability/incapacity
- Results in a congenital anomaly/birth defect (i.e., exposure to a medical product prior to conception or during pregnancy resulted in an adverse outcome in a child)
- Requires intervention to prevent permanent impairment or damage
- Overdosage (regardless of adverse outcome) of any study medication. An overdose is defined as the accidental or intentional ingestion of any dose of a product that is considered both excessive and medically important.
- Pregnancy

- Is an important medical event, defined as a medical event(s) that may not be immediately life threatening or result in death or hospitalization but, based upon appropriate medical and scientific judgment, may jeopardize the patient or may require medical or surgical intervention to prevent one of the other serious outcomes listed in the definition above. Examples of such events include, but are not limited to, intensive treatment in an emergency room or at home for allergic bronchospasm, or blood dyscrasias or convulsions that do not result in hospitalization.

The SAE reporting period begins once study drug treatment is initiated to within 30 days following cessation of treatment. AEs should be followed to resolution or stabilization, and reported as SAEs if they become serious. This also applies to patients experiencing AEs that cause interruption or discontinuation of investigational product, or those experiencing AEs that are present at the end of their participation in the study. Such patients should receive post-treatment follow-up as appropriate. If an ongoing AE changes in its severity or in its perceived relationship to study drug, a new AE entry for the event should be completed.

Additionally, any serious adverse event considered by an investigator to be possibly, probably, or definitely related to the investigational product that is brought to the attention of the investigator at any time outside of the time period specified in the previous paragraph also must be reported within 24 hrs of the site becoming aware of the event to the IRB and ProductLife Ltd using the forms provided by Medivation Inc. for this purpose.

Medical and scientific judgment should be exercised in deciding whether expedited reporting is appropriate in other situations, such as important medical events that may not be immediately life-threatening or result in death or hospitalization but may jeopardize the patient or may require intervention to prevent one of the other outcomes listed in the definition above. These should also usually be considered serious.

Note: The term "life-threatening" in the definition of "Serious Adverse Event" refers to an event in which the patient was at risk of death at the time of the event; it does not refer to an event that hypothetically might have caused death if it were more severe.

An **Unexpected Adverse Event** is not listed in the current US Package Insert may be mentioned in the package insert, but differs from the event because of greater severity or specificity.

Causality is a determination of whether there is a reasonable possibility that the drug may have caused or contributed to an adverse event. It includes assessing temporal relationships dechallenge/rechallenge information, association (or lack of association) with underlying diseases, and the presence (or absence) or a lack of one or more likely causes.

The Investigator must attempt to determine if an adverse event is in some way related to the use of the study drug. This relationship should be described as follows:

Unlikely: The event is clearly due to causes distinct from the use of the study drug, such as a documented pre-existing condition, the effect of a concomitant medication, a new condition which, based on the pathophysiology of the condition, and the pharmacology of the study drug, would be unlikely related to the use of the study drug.

Possible: The event follows a reasonable temporal sequence from administration of the study drug or the event follows a known response pattern to the study drug *BUT* the event could have been produced by an intercurrent medical condition which, based on the pathophysiology of the condition,

and the pharmacology of the study drug, would be unlikely related to the use of the study drug or the event could be the effect of a concomitant medication

Probable: The event follows a reasonable temporal sequence from administration of the study drug and the event follows a known response pattern to the study drug AND the event cannot have been reasonably explained by an intercurrent medical condition *or* the event cannot be the effect of a concomitant medication

Definite: The event follows a reasonable temporal sequence from administration of the study drug, the event follows a known response pattern to the study drug and based on the known pharmacology of the study drug, the event is clearly related to the effect of the study drug

Unknown: Based on the evidence available, causality cannot be ascribed

